**SPONSOR / FUNDING AGENCY**

*Internally Funded*

**VERSION NUMBER/DATE**

*Version 3 2/12/2020*

**REVISION HISTORY**

*This is revision number as submitted to the IRB.*

Revision #	Version Date	Summary of Changes	Consent Change (Yes/No)
1	1/14/2020	Clarified sample collection protocol and reasoning. Also added additional information regarding randomization and updated inclusion/exclusion criteria.	Yes

2	1/28/2020	Clarified statistical plan for research study including power analysis and made blood draw language consistent.	Yes
3	//2020	Extended post-operative surveys out to 1 year post-op. Added a baseline blood draw after induction of anesthesia. Also added standardization of tourniquet pressures across providers set to 275 mmHG (within SOC). Lastly, added two references to support the standardization of tourniquet pressures across all study patients across all 3 providers.	Yes
4	3/12/2020	Study design changes: Allowing morphine in PACU/post op and not allowing Toradol (Ketorolac) or Celecoxib in PACU/post op. Clarified that post-op blood draws will only be done on [name] 1 st and 2 nd case patients to ensure adequate processing availability by the research team. Study blinding will now be double-blind instead of single-blind. Changed the timings of the blood draws in order to better capture the variable of interest (baseline, 15 minutes after tourniquet is released, and 10 hours post-op). Lastly, the research team removed the gathering of bone & soft tissue samples from this study.	
5	5/8/2020	Updated exclusion criteria to include patient must be able to get general and spinal anesthesia.	
6	10/9/2020	Increased BMI cutoff from 35 to 38 for inclusion/exclusion criteria. Added exclusion criteria for same-day discharge patients.	

## 1. Purpose of the Study / Objectives

The purpose of this study is to determine if IO morphine decreases pain, inflammatory markers, and post-operative opioid use in total knee arthroplasty (TKA) patients.

- Aim 1: IO morphine will significantly reduce patient pain in the post-operative period after primary TKA.
  - Sub aim: IO morphine will cause significantly higher levels of morphine within the joint compared to current standard of care.
- Aim 2: IO morphine will decrease systemic inflammatory markers in the post-operative period after primary TKA.
- Aim 3: IO morphine will result in significantly less post-operative oral opioid use, and achieve superior outcomes such as increased range of motion (ROM).

## 2. Background

Following total knee arthroplasty (TKA), orthopedic surgeons must provide medication to control postoperative pain. Pain can be due to inflammation caused from tissue trauma, or nerve injury. Traditionally, opioids have been used as the sole pain management medication. Opiates reduce pain levels because they bind to opioid receptors inside and outside of the central nervous system. However, because the underlying physiology of pain is both neurogenic and inflammatory, the medications given should be multimodal. For example, cyclooxygenase-2-specific anti-inflammatory agents that are given pre-operatively, inhibit prostaglandin synthesis, and therefore decrease inflammation and pain in the immediate post-operative period.

Prior studies have explored if tissue or intra-articular injections with pain medications have effects on post-operative pain levels. Compared to patients with no intra-operative pain medication injection, patients that had intra-articular or soft tissue injections of a combination of bupivacaine, epinephrine, and morphine, had significant better pain control in the immediate post-operative period. Other studies have demonstrated that after receiving intra-articular injections, the need for post-operative narcotics decreased.

Though there are studies that have proven a beneficial effect of intra-operative medications, there have also been multiple studies that did not detect any difference in pain ratings in the immediate post-operative period. Therefore, it is still widely debated among orthopedic surgeons if intra-articular injections of pain medications reduces pain, decrease inflammation, and reduced use of opioids in the post-operative period.

Though studies have examined the effect of intra-articular morphine injection on pain, they have not determined if the level of morphine in the bone is higher compared to levels obtained intravenously. In addition, studies have not demonstrated if morphine has an effect on the inflammatory environment post-operatively. However, following cardiopulmonary bypass surgery, it was determined that morphine decreases the inflammatory response after surgery. Levels of a variety of inflammatory cytokines (IL-6, IL-8, CD11a, CD11b, CD11c, and CD18) were decreased among the patients that received morphine compared to patients that did not.

In addition oral opioids have many side effects including somnolence, depression of the brainstems control of the respiratory drive, urinary retention, nausea and vomiting, constipation, and ileus. In addition, as orthopedic surgery is progressing, patients are being discharged from the hospital 12-24 hours after surgery. This dramatic reduction in hospital stay makes it imperative to find a long lasting pain medication in the immediate post-operative period.

## 3. Study Design

This study is a double-blind randomized controlled trial with two arms. The control group will receive an intraosseous (IO) injection of antibiotics as per [name], [name], and [name] standard of care for primary TKA patients. The experimental group will receive an IO injection of antibiotics mixed with 10 mg of morphine. A research coordinator on the study team will inform the circulator nurse present in the OR during the study patient's case about which group (morphine or no morphine) the patient is in. The circulator nurse will then be instructed to place morphine into the surgical field during the mixing process of the intraosseous solution without notifying the surgeon to ensure the double blind. Patient's post-operative pain levels, pain medication consumption, side effects to pain medications, and range of motion will be recorded for 14 days following surgery.

Patient outcomes will also include pain levels, post-operative pain medication use, and post-operative ROM.

The anticipated total number of participants is 84 with 42 patients being in each group. The maximum number of subjects who will be enrolled is 84 patients (i.e. give consent to participate) at this site.

Participants will be randomized into either the control group or the experimental group by an excel-based software program.

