### **Baseline and Post-op Blood Samples:**

Systemic sample – Blood draws will only be done with [name] patients that decide to participate in the study if they are the first or second case of the day. Three blood draws will be taken in these patients including just after induction of anesthesia, 15 minutes after the tourniquet is released, and 10 hours post op. The 10hr post-op blood draw timing will be based on the timing of the intraosseous injection. Serum samples will be used to measure inflammatory cytokines IL-6 and IL-8, and expression of CD11a, CD11b, CD11c, and CD18 as well as the systemic level of morphine present in the blood. Only these specific study patients will be having blood draws done due to the 10 hr post-op draw needing to be processed within 30 minutes of the draw. Blood samples will be collected in EDTA glass tubes by Houston Methodist nursing staff or a qualified member of the research team (eg. physician, fellow, or resident). Up to 10 ml of blood will be collected per time point.

For our primary outcome variable of VAS recorded pain, power analysis was performed using JMP statistics software utilizing data extracted from prior work done on the average VAS-Pain scores for TKA patients.

The statistical model for this investigation to be utilized in this investigation is a 2(Treatment) x 2(Time-point) mixed model analysis of covariance with repeated measures, co-varied on pre-operative VAS scores recorded on the day of surgery. Although there will be several days of VAS recorded out to 14-days post-surgery, the statistical question for pairwise comparisons will be to determine (1) how pain recorded on each subsequent day compares back to initial baseline (pre-operative) values within each group (treatment vs control) and (2) how each group compares to each other at the same measurement time-point. Therefore, each subsequent day will be modeled separately against the baseline value.

From the reference cited above, the 3-day average VAS score immediately following TKA was 3.2 cm (standard deviation, 2.0cm). The minimum detectable change (MDC) to detect will be set at 1.6cm as described in the literature.

The primary hypotheses of the study is that the treatment group will experience a reduction in post-operative pain compared to the control group. Based on the previous literature listed above, for a power analysis of 2 groups across 2 time-points, to detect a MDC of 1.6cm at a statistical

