## Study Intervention

This study is evaluating whether a 10mg intraosseous injection of morphine will help reduce inflammatory markers following surgery as well as reduce pain and pain medication use in patients undergoing primary total knee arthroplasty when compared with patients receiving the current standard of care for primary total knee arthroplasty. In the post-operative period study patients will have their post-operative opioid consumptions monitored while in the hospital and for 14 days following their surgery. Study patients will not be allowed Ketorolac or Celecoxib (Toradol), both non-steroidal anti-inflammatories (NSAIDs), in the PACU / post-operative period following their total knee replacement. This is being done because the research team wishes to standardize the post-operative care protocols across all 3 providers participating in the study since not all prescribe NSAIDs in the post-operative period following TKA. Additionally, there is no method for NSAIDs like Ketorolac or Celecoxib to be converted into morphine equivalence scores and thus would prevent accurate quantification of pain relief provided in the post-operative period.

Should the patient suffer any side-effects from the IO morphine injection they will have all of the necessary care provided to them. This study will require the patient to consent to a number of study-related items including that do not fall under their usual standard of care:

- Filling out study surveys (PROMIS Global Health SF v1.1 and KOOS JR) at pre-op, 2 weeks post op, 8 weeks post op, and 1 year post-op. The surveys will be sent through RedCap.
- Blood draws to measure systemic levels of inflammatory cytokines right after induction of anesthesia, 15 minutes post tourniquet release, and 10 hours post op. This sample will be collected by a qualified Houston Methodist nurse or qualified member of the research team (ie physician/fellow/resident).

- Filling out a symptom journal for 2 weeks post op that will record pain, pain medication use, nausea (including emesis), and bowel movements.
- Lastly, patient range of motion will be recorded from their physical therapist' progress notes and at 2 week post-operative follow-up appointment.

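### The double blind rests on not telling the surgeon: the plan describes no matching addition in control cases and no concealment of the mixing step

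*Combined protocol and SAP*

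**What the plan says.** Section 3 (Study Design) opens with the claim: "This study is a double-blind randomized controlled trial with two arms". It then defines the arms. For control: "The control group will receive an intraosseous (IO) injection of antibiotics", following the participating surgeons' usual practice. For the experimental arm: "The experimental group will receive an IO injection of antibiotics mixed with 10 mg of morphine".

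The allocation reaches the operating room by word of mouth: "A research coordinator on the study team will inform the circulator nurse present in the OR during the study patient's case about which group" the patient belongs to. The circulator is then told to "place morphine into the surgical field during the mixing process of the intraosseous solution without notifying the surgeon to ensure the double blind". This is the only masking measure in the document.

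On outcomes, the plan refers to "For our primary outcome variable of VAS recorded pain", which patients enter daily in a 14-day symptom journal. Opioid consumption is followed in hospital and over the same 14 days. For motion, the Study Intervention section says that "patient range of motion will be recorded from their physical therapist' progress notes and at 2 week post-operative follow-up appointment".

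**The concern.** Keeping quiet about an event does not hide it. If a drug is passed onto the field in one arm and nothing is passed in the other, a person watching can tell the arms apart without being told. The plan presents this procedure as what secures the blind, so the question is about the procedure itself and not only about how fully it is written down.

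At stake is the comparison on outcomes that the surgical team can affect. A surgeon who believes that a patient had morphine might prescribe less opioid afterwards, or read range of motion more favourably. Either would favour the experimental arm and would be counted as a treatment effect under Aim 3. It could not be removed in the analysis once the data were collected.

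**Working it through.** No figure in the plan is in dispute, so the check is a reading of the relevant sections against one another.

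1. **What differs between the arms at the field.** By the two definitions in Section 3, the only difference is the added morphine, and it is added during mixing. The procedure is spelled out for morphine cases. For control cases no action by the circulator is described.

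2. **Whether masking is described elsewhere.** I looked for a placebo or saline addition, a matched volume, off-field or pharmacy preparation, a coded syringe, or screening of the mixing. The rest of Section 3, the Study Intervention section and Section 4 (Drugs, Biologics, Devices) contain none of these.

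3. **Who could learn the arm.** The coordinator and the circulator know it by design. The surgeon and others at the field could infer it if they see the step or notice that it is missing. The patient is unlikely to see it: the blood-sample section places the first draw just after induction of anesthesia, although the plan does not say when mixing takes place. The plan never lists which roles are meant to be blinded.

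4. **Which outcomes these people can reach.**
   - *Opioid use (Aim 3).* Section 2 gives surgeons the task of providing post-operative pain medication. The Study Intervention section standardizes care by barring two NSAIDs, but it sets no common opioid regimen that would limit discretion.
   - *Range of motion (Aim 3).* One of its two sources is the 2-week visit. The symptom-journal text in Section 3 says that this visit is with one of the three participating surgeons. The other source is the physical therapist's notes.
   - *Pain VAS (Aim 1).* The patient scores it. The arm would have to reach it through altered analgesia or through something said to the patient.

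5. **Effect of the remedy on sample size.** The plan asks for 35 per group to detect 1.6 cm with SD 2.0 cm, power 0.9 and alpha 0.05. A two-sided normal approximation gives 2 × (1.960 + 1.282)² × 2.0² / 1.6² = 32.8, so 33 per group, close to the plan's 35. A matched addition in controls changes none of these inputs.

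**The case against.** The strongest reply is that the absence of a control addition is inferred from silence. The plan never states that the circulator does nothing in control cases. It also does not say who mixes the solution, who can see it, or whether the containers can be told apart. A matching step may already exist in practice. This stands, and it rules out several stronger readings that a reader might draw:

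- *That the blind is certainly broken.* The documents show only that the described procedure could reveal the arm. They do not show that it does.
- *That the injected volume differs between arms.* No volume is given, so this would be a guess.
- *That the primary outcome is compromised.* The patient scores the VAS and probably does not see the mixing. Nothing suggests that surgeons will tell patients their arm.
- *That range of motion as a whole is exposed.* Part of it comes from therapists' notes. No section places the therapist at the field, and the plan does not say who measures motion at the visit.
- *That the bias can be sized.* Suppose the arm is recognizable in 25% to 100% of cases and opioid prescribing falls by 10% to 20% in those cases. The spurious reduction is then 0.25 × 0.10 = 2.5% to 1.00 × 0.20 = 20%. Neither input comes from the documents, and prescribing is not the same quantity as the consumption that patients record. The range only restates its assumptions.

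It can also be said that a sentence of clarification would be enough. That is true if a matched step is already in use. If not, clarification would only record a one-sided step.

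**Conclusion.** The concern holds in a limited form. The plan claims a double blind, describes an addition in one arm only, and relies on silence towards the surgeon to protect it. Followed as written, the procedure could disclose the arm to the surgeon and others at the field. The exposure falls mainly on post-operative opioid use and on range of motion at the 2-week visit. Any route to the primary VAS is indirect.

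The conclusion assumes that silence about control cases means that no matching step is planned, and that the mixing can be seen from the field. Both follow naturally from the text, but neither is stated. The size of any bias cannot be estimated from the documents. The point is worth acting on because the remedy is cheap and the bias could not be corrected afterwards. It is not a flaw that by itself invalidates the primary comparison.

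**What to change.** Amend Section 3 so that the circulator performs the same visible action in every case: adding an identical-looking syringe of equal volume, labelled with the study code only, containing morphine in the experimental arm and saline in the control arm. Have it prepared out of the surgical team's sight, and describe the procedure for both arms. If an equivalent step is already in use, writing it down is sufficient.

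In the same place, list who is blinded and who is not: patient, surgeon, scrub and recovery staff, physical therapist, whoever measures motion at the 2-week visit, coordinator and analyst. State also whether the coordinator who knows the allocation has later contact with patients or outcome data.

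The cost is one saline syringe per control case, at most 42 at the planned enrolment, plus slight extra work for whoever prepares the syringes. It does add a component to a control arm otherwise defined as usual care, and the protocol should say so. The morphine dose, sample size and analysis are unchanged.

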power of 0.9 ( $\alpha=0.05$ ), we will require a total of 35 patients per group (total of 140 observations). To account for a potential patient dropout rate of ~20%, we will aim to recruit 42 patients per group for a total of 84 patients.

The aforementioned statistical analysis will be performed at the end of each year to evaluate the efficacy of the intervention and to identify potential outliers in the data or any possible errors in data entry. Yearly analysis using the same statistical modeling will also be performed for our secondary outcome measures (tissue biomarkers) in order to prevent potential tissue sample and biochemical reagent degradation over time and to confirm the accuracy of the tissue analysis procedure performed.

Additionally, the study will stop recruiting if adverse effects is significantly different between the two treatment groups, or greater than the previously specified risks listed within the informed consent and protocol or if a new unanticipated adverse effect is discovered. Recruitment will be suspended if there are 5 similar adverse events in a row. The most serious risks include respiratory depression, apnea, circulatory depression, respiratory arrest, shock, and cardiac arrest. These risks are <1% of the population. More frequent adverse effects include sedation, lightheadedness, dizziness, nausea, vomiting, and constipation. Patients will be monitored for these side effects in the immediate post-operative period.

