## 6. Study Population

see pages 3-4 section 3 of this protocol.

Patients will be approached if they are undergoing TKA at Houston Methodist Hospital. Study coordinator, [name], or other qualified member of the research team (qualified to give informed consent) will determine if patients are eligible, and then consent the patient during their pre-operative visit.

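### Three surgeons take part, but no surgeon stratum is described and the VAS model has no surgeon term: a modest, cheaply recovered loss of precision

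*Combined protocol and SAP*

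**What the plan says.** **Allocation.** Section 3 (Study Design) plans 84 patients, 42 per arm, and describes the method in one sentence: "Participants will be randomized into either the control group or the experimental group by an excel-based software program". It mentions no strata, block sizes or surgeon factor, and it does not give the program's settings.

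**Model.** The statistical text under Baseline and Post-op Blood Samples specifies a treatment by time-point repeated-measures analysis of covariance, "co-varied on pre-operative VAS scores recorded on the day of surgery". No other covariate is named. The same modelling is to be used for the biomarkers. No separate model is given for opioid use or ROM, which belong to Aim 3.

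**Surgeons.** Three providers take part. The list of medical-record data in section 3, below the exclusion criteria, does not include the operating surgeon. The same part fixes one tourniquet pressure for all three, to limit outside influences on inflammatory markers and rehabilitation. The Study Intervention section bars ketorolac and celecoxib for all study patients because "not all prescribe NSAIDs in the post-operative period following TKA".

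**Blood subset.** Draws are limited to what reads as one surgeon's patients (the name is redacted), and only "if they are the first or second case of the day".

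**The concern.** The protocol itself treats surgeon as a possible source of variation, since it standardises two elements of care across the three providers. The design and the analysis do not follow this through. Pain, opioid use and ROM can all vary with the surgeon, through technique or through discharge prescribing. Without a stratum, one arm may by chance receive more of one surgeon's patients. Without a model term, that imbalance is not adjusted for, and the between-surgeon variance goes into the residual. With about 35 evaluable patients per arm, what is at stake is the precision of the primary pain comparison and how far the one realised allocation can be trusted.

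**Working it through.** **Inputs from the protocol.** Target difference: "The minimum detectable change (MDC) to detect will be set at 1.6cm". SD 2.0 cm, from "the 3-day average VAS score immediately following TKA was 3.2 cm (standard deviation, 2.0cm". Power 0.9, alpha 0.05 (two-sided assumed), 35 evaluable per group.

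**Assumed, because the protocol gives no figure.** Patients per surgeon, and the spread of mean VAS between surgeons.

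**1. The plan's own figure.** Normal approximation: n = 2 × 2.0² × (1.96 + 1.2816)² / 1.6² = 32.8, so 33 per group. The noncentral-t calculation needs 34 (power 0.902); 35 gives 0.910. The stated 35 is reproduced to within two patients. A one-sided test would need 27, which does not match.

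**2. Gain from adjustment, total SD held at 2.0 cm.** Take three equally frequent surgeons with equally spaced means and range R. The between-surgeon variance is [(R/2)² + 0 + (R/2)²] / 3 = R²/6, out of a total of 4.0.

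| R (assumed) | Surgeon variance | Share of total | Residual variance | Power at 35 per group |
|---|---|---|---|---|
| 0 cm | 0 | 0% | 4.00 | 0.910 |
| 1 cm | 0.167 | 4% | 3.83 | 0.921 |
| 2 cm | 0.667 | 17% | 3.33 | 0.951 |

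In sample-size terms the gain is 4.00/3.83 = 1.04 and 4.00/3.33 = 1.20, worth 4% and 20% more patients. Reducing the residual degrees of freedom from 68 to 66 does not change these powers at two decimals.

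**3. The same question with 2.0 cm as the within-surgeon SD.** Surgeon variance then comes on top. This was simulated with 4,000 trials per scenario, 35 per arm, surgeon means at -d, 0 and +d, and no baseline covariate.

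| Range 2d (assumed) | As planned (no stratum, no term) | Term alone | Stratum and term |
|---|---|---|---|
| 0 cm | 0.91 | 0.90 | 0.91 |
| 1 cm | 0.90 | 0.90 | 0.91 |
| 2 cm | 0.86 | 0.89 | 0.92 |
| 3 cm | 0.80 | 0.90 | 0.92 |

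**4. Type I error.** As planned, the simulated rate is 0.046-0.053, so there is no inflation, and the mean treatment estimate is on target. With stratification but no surgeon term, the rate falls to 0.032 (range 2 cm) or 0.022 (3 cm). The test becomes conservative, so the stratum and the term belong together.

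**5. Chance imbalance.** Assume a list that delivers exactly 42:42 without strata, and surgeon caseloads of 28/28/28, 42/21/21 or 50/24/10. The chance that some surgeon's share differs between arms by at least 10 percentage points is 38-55%; by at least 15 points, 16-27%; by at least 20 points, 6-10%. A 15-point shift between two surgeons whose patients differ by 1 cm moves the unadjusted difference by 0.15 × 1 = 0.15 cm. A 20-point shift with a 1.5 cm gap moves it by 0.20 × 1.5 = 0.30 cm. The target difference is 1.6 cm.

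**6. Arm split in the blood subset.** Its size is not stated. Under the same fixed 42:42 list, a split of 2:1 or worse has probability 31%, 16% and 7% for assumed sizes of 10, 16 and 20.

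**The case against.** The strongest reply is that the protocol has already dealt with the one practice difference it documents. Only NSAID prescribing is said to differ between the surgeons, and both named NSAIDs are barred for every study patient. The tourniquet pressure is described as within usual practice for all three, so fixing it does not show that they differed. No remaining surgeon effect on pain is documented. At a total SD of 2.0 cm the plan already has power 0.91 against a target of 0.90. All of this stands, and it limits the point to an improvement in precision.

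A reader might infer more, and the documents do not support it:

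- **That the trial is biased or its error rate inflated.** Randomisation removes systematic bias, and step 4 of the working shows type I error near 5%.
- **That the allocation is a coin flip, or that reaching 42:42 requires blocking within surgeon.** The program's settings are not given, and an unstratified shuffled list of 42 + 42 delivers 42:42 exactly. The accurate statement is that no stratification is described.
- **That the blood subset suffers from surgeon imbalance.** A one-surgeon subset cannot. What is left uncontrolled there is the arm split. A surgeon term also cannot be estimated in those models.

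The reply does not remove the core. Barring two drugs and fixing one pressure leaves technique and discharge opioid prescribing free to vary, and opioid use is itself an Aim 3 outcome.

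**Conclusion.** The point holds as a low-cost improvement in precision. No surgeon stratum is described, the model adjusts only for pre-operative VAS, and surgeon is not on the list of data to extract. The expected gain is small to moderate: power at 35 per group rises from about 0.91 to 0.92-0.95 if surgeon means span 1 to 2 cm within a total SD of 2.0 cm, and stays at about 0.91 if they do not differ. The larger losses in step 3 (planned power of 0.86 or 0.80) require surgeon means 2 to 3 cm apart on top of a within-surgeon SD of 2.0 cm, and nothing in the protocol documents such a spread. The size therefore rests on an assumed between-surgeon difference and assumed caseloads. That surgeon is left out of the described allocation and of the stated model does not depend on those assumptions.

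**What to change.** 1. Add the operating surgeon to the data to be extracted.
2. Generate the list in permuted blocks stratified by surgeon, and state this in section 3. Stratifying also limits uneven arm splits among the patients of the one surgeon whose early cases supply the blood subset, although it does not guarantee balance within that subset.
3. Add surgeon as a fixed effect to the VAS model and to the secondary models that include all three surgeons (opioid use, ROM). Leave it out of the blood-biomarker models, where it would be constant.
4. If enrolment has started, pre-specify the model term alone. In the simulation this keeps power at 0.89-0.90 across surgeon ranges of 0 to 3 cm. If surgeons do not differ at all, the price is about one point of power (0.91 to 0.90).

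Cost: 2 degrees of freedom, a new list, and a possible small departure from exactly 42:42 because of incomplete blocks. No extra patients or visits are needed.
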